10.4. SAS code for EQ-5D index utility scoring

```
/*=====*/;
/* Aim : Derive the EQ5-D index (utility) */;
/* Source for the algorithm : scoring EQ-5D health states (Rosalind Rabin */;
/* (cf. G:\_HE\PRO questionnaire\EQ5D\scoring\YorkTariffx.doc) */;
/* Note : UK based population (Dolan, 1997) */;
/* Author : [name] */;
/*=====*/;

data EUROQOL; set temp;
    profil= (10000*eqq1cd)+(1000*eqq2cd)+(100*eqq3cd)+(10*eqq4cd)+eqq5cd;
    eq5d=1;
*****Mobility*****;
if eqq1cd=2 then eq5d=eq5d-0.069;
if eqq1cd=3 then eq5d=eq5d-0.314;
*****Self-care*****;
if eqq2cd=2 then eq5d=eq5d-0.104;
if eqq2cd=3 then eq5d=eq5d-0.214;
*****Usual activities*****;
if eqq3cd=2 then eq5d=eq5d-0.036;
if eqq3cd=3 then eq5d=eq5d-0.094;
*****Pain/discomfort*****;
if eqq4cd=2 then eq5d=eq5d-0.123;
if eqq4cd=3 then eq5d=eq5d-0.386;
*****Anxiety/depression*****;
if eqq5cd=2 then eq5d=eq5d-0.071;
if eqq5cd=3 then eq5d=eq5d-0.236;

if (eqq1cd ne 1 or eqq2cd ne 1 or eqq3cd ne 1 or eqq4cd ne 1 or eqq5cd ne 1)
then eq5d=eq5d-0.081;
if (eqq1cd=3 or eqq2cd=3 or eqq3cd=3 or eqq4cd=3 or eqq5cd=3)
then eq5d=eq5d-0.269;
if (eqq1cd=. or eqq2cd=. or eqq3cd=. or eqq4cd=. or eqq5cd=.)
then eq5d=.;

run;
```

10.5. Exposure-Adjusted Analyses

To account for potentially differential exposure time, two types of exposure-adjusted analyses will be provided for analysis, namely, number of events per 100 patient-years and number of patients with at least one event per 100 patient-years.

Number of events per 100 patient-years

The number of events per 100 patient-years (NEPY) will be calculated as the number of events occurring in the population divided by the sum of the exposure over all patients (ie, total exposure) in the TEAE period.

$$NEPY = 100 \times \frac{\sum n_i}{\sum t_i}$$

where n_i is the number of events observed for patient i ; t_i is total TEAE exposure for patient i in person-year unit.

Number of patients with at least one event per 100 patient-years

The exposure-adjusted incidence rate (EAIR) is the expected number of patients with at least one specific adverse event per 100 patients taking the treatment for 1 year (52 weeks). The number of patients with at least one event per 100 patient-years will be calculated as the number of patients having a specific event divided by the total person-year among patients in the pool and at risk of an initial occurrence of the event. In particular, the EAIR is computed as follows:

$$EAIR = 100 \times \frac{n}{\sum t_i}$$

where n is the number of patients with the specific adverse event; it is a patient's exposure time in person-year unit. For each of the adverse events of interest, the exposure time for patients who have experienced the adverse experience will be defined as the time to first adverse experience, whereas the exposure time for those who have not had this adverse experience will be total duration of exposure in the TEAE period.

10.6. Search Criteria for TEAE of Special Interest/TEAE Syndrome

Below table is the search criteria for AESI under protocol amendment 4 and 5.

AESI	Search Criteria
Anaphylactic reactions	Narrow SMQ for “anaphylactic reaction”
Acute allergic reactions that require treatment	Narrow SMQ for “hypersensitivity” Action taken for AE=“medication” or “surgery” Note: Blinded manual adjudication of relevant PTs will be required by the study medical monitor, before database locks
Severe ISRs that last longer than 24 hours	-HLT = Injection site reactions - Severity = “severe” - duration of AE > 24 hours
Mycosis fungoides or other forms of cutaneous T cell lymphoma	-HLT = “Mycosis fungoides” • Includes LLT = Sezary syndrome • Includes LLT = Cutaneous T-cell lymphoma -PT = “Cutaneous T-cell dyscrasia
Any severe infection	-SOC = Infections and infestations -Severity = “severe
Any infection requiring treatment with parenteral antibiotics	-SOC = Infection and infestations -Action taken for AE = “medication” -ConMed: ATC3= “Antiinfectives” during the TEAE course (between start and stop dates), Route = IV, IM
Any infection requiring treatment with oral antibiotic/anti-viral/anti-fungal for longer than 2 weeks	-SOC = Infection and infestations -Action taken for AE = “medication” -Check CM: ATC3= “Antiinfectives” during the TEAE course (between start and stop dates), Route = PO and Treatment duration >14 days
Any clinical endoparasitosis	-HLT = Cestode infections -HLT = Helminthic infections NEC -HLT = Nematode infections -HLT = Trematode infection

AESI	Search Criteria
Any opportunistic infection ^a	The following HLTs plus PTs -HLT = Pneumocystis infection -HLT* = Fungal infections NEC -HLT* = Pseudallescheria infections -HLT = Herpes viral infections -HLT = Paracoccidioides infections -HLT = Sporothrix infections -HLT = Cryptosporidia infections -HLT* = Trypanosomal infections -HLT* = Campylobacter infections -HLT* = Shigella infections -HLT* = Vibrio infections Plus the following PTs -Polyomavirus-associated nephropathy -BK virus infection -Cytomegalovirus infection -Post transplant lymphoproliferative disorder -Progressive multifocal leukoencephalopathy -*Bartonellosis -Blastomycosis -Toxoplasmosis -Coccidioidomycosis -Histoplasmosis -*Aspergillus infection -Systemic candida -Oropharyngeal candidiasis -Cryptococcosis -Listeriosis -Tuberculosis -Nocardiosis -Mycobacterial infection -*Salmonellosis -*Hepatitis B -Herpes zoster -*Strongyloidiasis -Microsporidia infection -Visceral leishmaniasis -*Hepatitis C -Eczema herpeticum

AESI	Search Criteria
	-Kaposi's varicelliform eruption -Herpes zoster Note: *Blinded manual adjudication of relevant PTs under each of HLTs listed above will be required by the study medical monitor, before database locks
Suicidal behavior	Include the following PTs -Completed suicide -Suicidal ideation -Suicide attempt -Depression suicidal -Suicidal behavior

^a The definition of opportunistic infections is referring to the recent consensus guidance for opportunistic infections in the setting of biologic therapy (K L Winthrop et al, 2015)

Below table is the search criteria for AESI under protocol amendment 6/7/8.

AESI	Search Criteria
Anaphylactic reactions	For SMQ “anaphylactic reaction” An algorithmic approach will be used. A case must include either: 4. A narrow term (a term from Category A); 5. Patient with both a term from Category B AND a term from Category C ; 6. Patient with a term from Category D AND { a term from Category B - OR a term from Category C } For bullets 2 and 3, the search terms that are included under the SMQ for a particular event need to have the same start date (for e.g. if search shows cough (category B term) occurring at day 3 and urticaria (category C term) occurring at day 7, this event is not adjudicated as anaphylactic reaction as this is inconsistent with the clinical presentation of anaphylaxis as an acute event with simultaneous involvement of 2 or more body systems. Note: manual adjudication of relevant PTs will be required by the study medical monitor, before database lock

AESI	Search Criteria
Systemic or severe hypersensitivity reactions	
Hypersensitivity: Narrow SMQ for hypersensitivity excluding preferred term equal to dermatitis atopic or eczema
 
For systemic hypersensitivity, events in which 2 or more body systems are involved (as defined by System Organ Class) would be considered for adjudication based on further medical judgement
 
For severe hypersensitivity, an additional search will be done;
 
 - HLT = Injection site reactions - Severity = “severe” 
Note: manual adjudication of relevant PTs will be required by the study medical monitor, before database lock

Malignancy	
 • SMQ “Malignant tumours” • SMQ “Tumours of unspecified malignancy”
Helminthic infections	
-HLT = Cestode infections
 
-HLT = Helminthic infections NEC
 
-HLT = Nematode infections
 
-HLT = Trematode infection

Suicidal behavior	
Include the following PTs
 
 • Completed suicide • Suicidal ideation • Suicide attempt • Depression suicidal • Suicidal behavior
Any type of conjunctivitis or blepharitis or keratitis (only events that are either severe or serious)	
broad CMQ conjunctivitis (Conjunctivitis, Conjunctivitis allergic, Conjunctivitis bacterial, Conjunctivitis viral, Atopic keratoconjunctivitis, Blepharitis, Dry eye, Eye irritation, Eye pruritus, Lacrimation increased, Eye discharge, Foreign body sensation in eyes, Photophobia, Ocular hyperaemia, Conjunctival hyperaemia, Xerophthalmia);
 
Blepharitis PTs (Blepharitis, blepharitis allergic);
 
Keratitis PTs (Keratitis, Allergic keratitis, Ulcerative keratitis, Atopic keratoconjunctivitis, Herpes ophthalmic, Ophthalmic herpes simplex);
 
AND
 
 • Serious AE= “Yes” OR Severity= “severe” 
Note: manual adjudication of relevant PTs will be required by the study medical monitor, before database lock.

¹ The search criteria are meant to assist the process of identification of TEAE of Special Interest/TEAE Syndrome. However, since these criteria might not be exhaustive in some cases or may not be specific in other cases. Hence an additional review of all PTs in the database may be performed by the Medical monitor, based on medical judgement, to identify any TEAE of Special Interest/TEAE Syndrome that might have been missed by the criteria or to identify any TEAE may be inaccurately assigned as AESI by the algorithmic search

10.7. Process to Derive Data Cut-off for the First Step Analysis

Database lock of the first step analysis for R668-AD-1225 study is planned for 05-May-2016 with data cut-off date 11-Apr-2016.

The data cutoff algorithm will be applied to the raw datasets extracted from Electronic Data Capture (EDC) and IVRS system.

I. Patients to be included for the first step analysis

1. Include enrolled patients with date of enrollment \leq 11Apr2016 inside ELIG1 raw dataset.
2. Include screen failure patients with record date \leq 11Apr2016 inside ELIG raw dataset.

Note: only these patients' data will be included in the first step analysis. Hence patients who are under screening and do not enroll prior to the data cut-off date will not be included in the first step analysis.

II. Data recorded during the screening period:

The following data recorded during the screening period for patients identified in step (I) do not need data cut-off. All data for patients identified in step (I) included in the final locked data transfer will be used for the first step analysis.

Informed consent

Inclusion/exclusion

Medical history

Demographics

Previous AD study information

III. Data collected through IVRS

1. All diary data collected on or before 11-Apr-2016 will be kept for the first step analysis.
2. For the kit allocation dataset, all records will be kept for the first step analysis.

IV. Visit dependent data:

All visit dependent data on or before 11-Apr-2016 will be kept for the first step analysis. All visit dependent data collected later than 11-Apr-2016 will not be included in the first step analysis datasets. Unscheduled visits with a date on or before 11-Apr-2016 will be kept on the first step analysis.

V. Visit independent/Event based data:

This includes adverse events, concomitant/prior medication and procedure:

All event records with a start date later than 11-Apr-2016 will be censored (this includes incomplete dates when the incomplete date is without any doubts later than 11-Apr-2016, e.g. the incomplete date is May 2016).

Records with a start date earlier or on 11-Apr-2016 will be kept (this includes incomplete dates when the incomplete date is earlier than 11-Apr-2016 or in case of doubts, e.g. the incomplete date for an event is April 2016, or only year 2016 or even a missing date).

For the events included in the first step analysis cut-off, several adaptations to the data will be made:

- Adverse Events:
 - If a stop date of adverse event is specified and earlier or equal to 11-Apr-2016 then the record will not be changed.
 - If a stop date of adverse event is specified and later than 11-Apr-2016, then the stop date will be deleted (set to missing) and the outcome of the adverse event (SAS variable AEOUT/AEOUTN) will be set to missing, AE ongoing status will be set to Yes.
 - If no stop date is specified and the outcome is either not yet reported (AEOUT/AEOUTN is blank) or is reported (AEOUT in (recovering/resolving, not recovered/not resolved, unknown)), then the outcome will be set to missing (AEOUT/AEOUTN is blank)
- Concomitant medication/procedure:
 - If a stop date is reported which is earlier than or on 11-Apr-2016, the record will not be changed.
 - If a stop date is reported which is later than 11-Apr-2016, the date will be set to missing and ongoing status will be set to Yes.

10.8. Process to Derive Data Cut-off for the Second Step Analysis

Database lock of the second step analysis for R668-AD-1225 study is planned for 14-Feb-2019 with data cut-off date 01-Dec-2018 for ongoing patients in Poland, Finland, Russia, New Zealand, and Singapore. All data for patients from remaining countries will be included for analysis.

The data cutoff algorithm will be applied to the raw datasets extracted from Electronic Data Capture (EDC) and IVRS system.

I. Patients to be included for the second step analysis

All screened patients will be included for analysis.

II. Data recorded during the screening period:

All data recorded during the screening period will be included for analysis.

III. Data collected through IVRS

1. All diary data collected on or before 01-Dec-2018 for ongoing patients in Poland, Finland, Russia, New Zealand, and Singapore will be kept for the second step analysis.
2. All diary data for patients from rest countries will be included for the second step analysis.
3. For the kit allocation dataset, all records will be kept for the second step analysis.

IV. Visit dependent data:

All visit dependent data on or before 01-Dec-2018 for ongoing patients in Poland, Finland, Russia, New Zealand, and Singapore will be kept for the second step analysis. All visit dependent data collected later than 01-Dec-2018 will not be included in the second step analysis datasets. Unscheduled visits with a date on or before 01-Dec-2018 will be kept on the second step analysis.

V. Visit independent/Event based data:

This includes adverse events, concomitant/prior medication and procedure:

All event records with a start date later than 01-Dec-2018 will be censored (this includes incomplete dates when the incomplete date is without any doubts later than 01-Dec-2018, e.g. the incomplete date is December 2018).

Records with a start date earlier or on 01-Dec-2018 will be kept (this includes incomplete dates when the incomplete date is earlier than 01-Dec-2018 or in case of doubts, e.g. the incomplete date for an event is November 2018, or only year 2018 or even a missing date).

For the events included in the first step analysis cut-off, several adaptations to the data will be made:

- Adverse Events:
 - If a stop date of adverse event is specified and earlier or equal to 01-Dec-2018 then the record will not be changed.
 - If a stop date of adverse event is specified and later than 01-Dec-2018, then the stop date will be deleted (set to missing) and the outcome of the adverse event (SAS variable AEOUT/AEOUTN) will be set to missing, AE ongoing status will be set to Yes.
 - If no stop date is specified and the outcome is either not yet reported (AEOUT/AEOUTN is blank) or is reported (AEOUT in (recovering/resolving, not recovered/not resolved, unknown)), then the outcome will be set to missing (AEOUT/AEOUTN is blank)
- Concomitant medication/procedure:
 - If a stop date is reported which is earlier than or on 01-Dec-2018, the record will not be changed.
 - If a stop date is reported which is later than 01-Dec-2018, the date will be set to missing and ongoing status will be set to Yes.

10.9. Algorithm to Add Not Reported Home Study Drug Injection Records Based on Drug Accountability Data for First Step analysis

Background and Rationale:

The R668-AD-1225 study is a multicenter, open-label extension study to assess the long-term safety and efficacy of repeat doses of dupilumab in adults with moderate-to-severe AD who have previously participated in controlled studies of dupilumab. Study drug was dupilumab 300 mg, administered weekly via subcutaneous injections. During the study, patients were provided the option to administer the study drug outside the clinic, in which case they were dispensed drug supplies for up to 4 weeks at monthly visits and up to 8 weeks at bimonthly visits. Study drug administration and drug accountability were recorded in several sources:

The weekly study drug injections were reported in two sources.

- EDC where on-site injections were reported.
- IVRS where patients reported their weekly injections taken at home.

The dispensation and return of study drug supplies (used, partially used or unused) were reported in:

- EDC where study drug kit dispense/return data was captured

A considerable number of home-injections were not reported through IVRS system, but were actually taken by the patients. This is supported by drug accountability records, which documented the administration of study drug via the dispensation of drug supplies and the return of used kits. The purpose of this appendix is to provide the algorithm for creating a more complete and accurate study drug administration record for the analysis by incorporating these data sources.

Algorithm:

1. Between the scheduled on-site dispensing visit and next on-site return visit, identify all kits dispensed including the one(s) dispensed at the unscheduled visit(s) between, and all kits returned.
2. Identify kits used between these 2 visits and count number of kits used.
 - If the question “If all vials are empty” from CRF was answered as “Yes”, then it was assumed that all returned kits were taken by the patient.
 - If the question “If all vials are empty” from CRF was answered as “No”, use the information from excel spreadsheet R668AD1225 Kit not empty.xls to identify which kits were not used. For each kit return record,
 - I. If the column ‘Adjudicated by team, if total volume was injected’ was Yes, then it was assumed that all returned kits were taken by the patient.
 - II. If column ‘Adjudicated by team, if total volume was injected’ was No, then kits identified starting from column “Kit number not used” were the returned kits not taken by the patient.
3. Identify the dose injection records reported in EDC and IVRS satisfying condition: date of dispensing visit \leq date of injection $<$ date of next on-site return visit, then count number of injections between visits.
4. If the number of injections in step #3 is less than the number of kits used in step #2, then add the not reported injections into SDTM.EX dataset. These not reported injections will be identified using variables in SUPPEX with QNAM=DATAORG and QVAL=”Added by drug accountability”. The Treatment variable (EXTRT) and dose variable (EXDOSE) will be populated for the newly added injections based on last observation carry forward (LOCF) method.
5. If the number of injections in step #3 is equal to or larger than the number of kits used in step #2, then no new injection record will be added into SDTM.EX dataset.

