2.3. Study Plan (Schedule of Study Assessment)

The study consists of a screening period, a treatment period and a follow-up period. The dose level, the duration of treatment period and follow-up period were modified for the study through several protocol amendments. These modifications are outlined in [Table 1](#).

Table 2: Study dose level and study duration under each protocol version

Protocol Version	Country	Dose Level (mg)	Duration of Treatment Period	Duration of Follow-up period
Original and amendment 1	Global	200	100 weeks	16 weeks
Amendment 2 and 3	Global	300	100 weeks	16 weeks
Amendment 4	Global	300	148 weeks or until commercially available	16 weeks
Amendment 5 and 6	Great Britain	300	100 weeks	16 weeks
Amendment 6	Global, Hungary, Japan	300	148 weeks or until commercially available	16 weeks
Amendment 7	Global, Hungary	300	148 weeks or until commercially available	12 weeks
Amendment 7*	France, Germany, Poland, Japan	300	Extend treatment period through approximately 31 December 2017	12 weeks
Amendment 7	Great Britain	300	100 weeks	12 weeks
Amendment 8**	Poland, Finland	300	Extend treatment period to up to 5 years (week 260)	12 weeks
Amendment 8**	France	300	Extend treatment period to approximately September 2018	12 weeks

* Note: Under protocol amendment 7 for France, Germany, Poland and Japan, patients who had already completed the End of Treatment visit under protocol amendment 6 were permitted to resume treatment with study drug. Patients who had completed the End of Study visit were permitted to re-enter the study. The treatment period ended for all patients in these countries on or about 31 December 2017.

** Note: Patients in Poland, Finland and France who had completed their End of Treatment/End of Study visit as per amendment 7 were permitted to resume treatment/re-enter the study provided that no more than 12 weeks had elapsed since their End of Study visit. The duration of the overall treatment period for patients in Poland and Finland was extended to 5 years, and to September 2018 for patients in France.

The study flow diagrams under protocol amendment 7 and 8 are provided in [Figure 2](#), [Figure 3](#), [Figure 34](#) and [Figure 35](#) below:

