7. INTERIM ANALYSIS

This is an open-label extension study. No formal interim analyses will be planned for this study.

A first step analysis was performed to support the submission of market application for dupilumab in AD indication in third quarter of year 2016. All data prior to the cutoff date (11Apr2016) were included in this analysis. The process to derive the data cut-off for the first step analysis is outlined in [Appendix 10.7](#).

A second step analysis will be performed in first quarter of year 2019 in order to have long term data of dupilumab in AD indication. All data prior to the cutoff date (around 01Dec2018) for patients in Poland, Finland, Russia, New Zealand, Singapore and all data for patients from remaining countries will be included in this analysis. Patients from remaining countries will either complete or early withdrawn from the study at time of database lock. The process to derive the data cut-off for the second step analysis is outlined in [Appendix 10.8](#).

Future analyses will be performed to support the subsequent regulatory filings. The details and data cutoff date will be specified in future SAP addendum.

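### SAP 10.8 Part V, and Part IV if read literally, applies the 01-Dec-2018 cut-off without the country limit set by Section 7 and the opening of 10.8

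*SAP*

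**What the plan says.** The opening of SAP 10.8 sets a "data cut-off date 01-Dec-2018 for ongoing patients in Poland, Finland, Russia, New Zealand, and Singapore" and then states "All data for patients from remaining countries will be included for analysis". Section 7 gives the same rule for the remaining countries, "all data for patients from remaining countries will be included in this analysis", and explains their status: "Patients from remaining countries will either complete or early withdrawn from the study at time of database lock". For the timing of the lock, 10.8 says "Database lock of the second step analysis for R668-AD-1225 study is planned for 14-Feb-2019".

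The detailed parts of 10.8 follow this scope unevenly:

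- **Part III (IVRS data)** has one line for ongoing patients in the five countries and a separate line keeping all diary data from the rest.
- **Part IV (visit data)** names the five countries in its keep sentence. Its exclusion sentence has no country limit: "All visit dependent data collected later than 01-Dec-2018 will not be included in the second step analysis datasets".
- **Part V (adverse events, medications, procedures)** names no country: "All event records with a start date later than 01-Dec-2018 will be censored". Its adaptations of kept records also name none. They set later AE stop dates and the matching outcomes to missing, treat later medication and procedure stop dates the same way, and blank the outcome of any AE that has no stop date and is recorded as recovering, not recovered or unknown.

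**The concern.** 10.8 is the algorithm applied to the raw EDC and IVRS extracts, so its detailed parts are what a programmer would code. Part V, coded as it stands, contradicts the scope set a few lines above it and in Section 7.

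The data at stake are late follow-up events. SAP 4.6.1 counts every AE with onset in the treatment or follow-up period as a TEAE, and TEAE incidence and rate form the primary endpoint. Remaining-country events starting after 01-Dec-2018 would drop out of it. If Part IV is also read literally, visits after that date go too. If instead visits are kept in full while Part V is coded literally, follow-up time stays complete and event counts are truncated. The events-per-patient-year figure in SAP 10.5 would then be biased downward.

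Separately, final AE outcomes would be erased for patients whose data are meant to be complete.

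**Working it through.** The plan states no figure that depends on this rule, so the check is a comparison of text followed by date arithmetic.

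**1. The rules side by side**

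| Place in SAP | Five named countries | Remaining countries |
|---|---|---|
| Section 7 | cut off around 01-Dec-2018 | all data included |
| 10.8 opening | cut off, ongoing patients | all data included |
| 10.8 Part III | cut off, ongoing patients | all diary data included |
| 10.8 Part IV, keep sentence | kept up to the cut-off, ongoing patients | not mentioned |
| 10.8 Part IV, exclusion sentence | no country stated | no country stated |
| 10.8 Part V, start-date rule | no country stated | no country stated |
| 10.8 Part V, stop-date and outcome rules | no country stated | no country stated |

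Parts IV and V closely follow the first-step rules in 10.7, which were written for one global cut-off on 11-Apr-2016 and needed no country limit. Part V of 10.8 still introduces its adaptations as applying to the first-step cut-off. This points to text carried over without the new scope.

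**2. Length of the exposed interval**

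Planned lock minus cut-off: 14-Feb-2019 − 01-Dec-2018 = 30 + 31 + 14 = 75 days, or 75/7 = 10.7 weeks. Section 7 requires remaining-country patients to have finished by the lock, not by the cut-off, so records in this interval are possible.

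**3. France as an example**

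France is not one of the five countries. SAP 2.3, Table 2, gives its amendment 8 treatment period as "Extend treatment period to approximately September 2018", with 12 weeks (84 days) of follow-up. End-of-study date = last dose + 84 days:

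- last dose 1 September → 24 November (before the cut-off)
- last dose 8 September → 1 December (on the cut-off)
- last dose 9 September → 2 December (after)
- last dose 30 September → 23 December (22 days after)

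A last dose after 8 September 2018 therefore puts the scheduled end-of-study visit, and the last part of the TEAE period, beyond the cut-off.

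**4. What each rule changes**

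- *Start-date rule (Part V):* removes AEs with onset after 01-Dec-2018, and so changes TEAE counts. AEs that began on or before that date stay in.
- *Stop-date and outcome rules (Part V):* act on AEs that are kept. TEAE status depends on onset, and the two rates in 10.5 use event counts, exposure time and time to first event. None of these uses the stop date or outcome of a kept AE.
- *Outcome rule for AEs without a stop date (Part V):* has no date condition of its own. It reaches patients who completed well before December 2018.

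**The case against.** The strongest reply is that the scope is stated at the head of the same appendix and again in Section 7, so the later parts can omit it. For Part IV this has real force. Its exclusion sentence directly follows a sentence limited to the five countries and can be read as completing it. A fully literal Part IV would also keep no remaining-country visit at any date, which plainly is not meant. Part V has no preceding sentence from which to take the limit, and Part III shows the authors writing out the split where they applied it. For Part V the reply therefore explains the intent but does not supply the missing rule.

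Three further points stand. The second step is descriptive, with no hypothesis tested. The data remain in the database for later analyses. Blanking stop dates and outcomes leaves the primary endpoint unchanged.

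A reader might go further than the documents allow in three ways:

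- *That the SAP orders the cut-off in every country.* It never says so; this is an inference from a missing limit, against a scope stated twice.
- *That completed patients in general lose their last safety visit.* Only remaining-country records dated after 01-Dec-2018 are at risk of deletion, and for visits only on the literal reading of Part IV.
- *That about 73% of French end-of-study visits would go.* The 22 of 30 September days with a last dose after the 8th is a share of calendar days under an assumed even spread. It is not a share of patients. The SAP says only approximately September and does not reproduce the French schedule. The Poland/Finland schedule allows ±30 days around the 84-day visit. If that applied in France (assumption), a 1 September last dose could give a visit as late as 24 December and a 30 September last dose one as early as 23 November. The share could then lie anywhere from 0% to 100%.

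**Conclusion.** The point holds as an internal contradiction that gives a wrong result if Part V is programmed as written. It is certain for Part V and depends on the reading for the exclusion sentence of Part IV. The intended rule is almost surely the one in Section 7 and the opening of 10.8.

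The exposed records are remaining-country events with onset in the 75 days after the cut-off, together with visits in that interval if Part IV is taken literally. The effect on TEAE incidence and rates cannot be sized, because the documents give no count of remaining-country patients still in follow-up then. SAP 2.3 gives only about 272 patients with a second treatment gap across Poland, Finland and France combined, against 2678 enrolled. The French example assumes last doses in September 2018 and a visit at exactly 84 days. The loss of AE outcomes does not depend on that example, but it is a reporting matter and not an endpoint effect.

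A related mismatch needs the same edit: Section 7 cuts off patients in the five countries, whereas 10.8 cuts off only ongoing patients there. Completed or withdrawn patients in those countries have no single rule.

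**What to change.** In SAP 10.8:

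1. Limit the exclusion sentence of Part IV, and all of Part V including the stop-date and outcome adaptations, to the cut-off population in Poland, Finland, Russia, New Zealand and Singapore.
2. Add to Parts IV and V a line matching item 2 of Part III: all visit and event data from the remaining countries are kept, with no cut-off and no blanking.
3. Use one definition of the cut-off population in Section 7 and 10.8, stating whether completed or withdrawn patients in the five countries are cut off or kept in full.
4. Correct the reference to the first step in Part V's adaptation sentence to the second step.

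The cost is SAP wording only; no design or sample-size figure changes. If the second-step datasets have already been built, confirm which rule the programs applied. If Part V was coded literally, rerun the AE, medication and procedure outputs.
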